#### **5.8.2.6. Standard of Care Treatment for Underlying Cancer or Bone Metastasis (after Week 8)**

Between Week 8 to Week 32, if treatment for underlying cancer or bone metastasis needs to be initiated or changed (refer to [Section 5.8.2.3](#)), the study clinician should be informed so that guidance may be provided as to whether the subject should be withdrawn from study treatment and entered in the Early Termination Follow-Up period. Following Week 32, cancer or bone metastasis treatment may be instituted in accordance with standard of care without prior consultation of the study clinician.

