#### **4.2. Exclusion Criteria**

Subjects with any of the following characteristics/conditions will not be included in the study:

1. The subject's pain is related to an oncologic emergency such as bowel obstruction/perforation, spinal cord compression, epidural metastasis, or fracture or impending fracture of weight bearing bone.
2. The subject has brain metastasis or leptomeningeal metastasis.
3. Presence of hypercalcemia at Screening (confirmed by a repeat test if needed), defined as albumin-corrected serum calcium concentration of  $\geq 12$  mg/dL. If

measured albumin is <4.5 gm/dL, corrected calcium (mg/dL) = measured calcium (mg/dL) + 0.8 x (4.5 gm/dL-measured albumin in gm/dL).

4. The subject's pain is primarily classified as neuropathic, visceral or unknown in nature, has resulted from prior cancer therapy, is due to infection or is otherwise not predominantly related to a bone metastasis.
5. Systemic treatment for the primary malignancy or bone metastasis, including chemotherapy, hormonal treatment (eg, gonadotropin-releasing hormone (GnRH) agonists or antagonists), bisphosphonates and denosumab started within 30 days of the first day of the Baseline Assessment Period.

Chemotherapies associated with peripheral neuropathy (ie, paclitaxel, docetaxel, oxaliplatin, cisplatin, vincristine, thalidomide or bortezomib), are prohibited during study period from 30 days prior to the first day of the Baseline Assessment Period to Week 48.

6. Receipt of radiopharmaceutical treatment or radiotherapy for treatment of bone metastasis within 30 days of the first day of the Baseline Assessment Period. Subjects who are candidates for external beam radiotherapy for painful bone metastasis should not be considered for this study in lieu of external beam radiotherapy.
7. Initiation or unstable dose of concurrent adjuvant analgesics such as single-agent acetaminophen (paracetamol), serotonin norepinephrine reuptake inhibitors (SNRI), tricyclic antidepressants, anticonvulsant medication, corticosteroids, or muscle relaxants within 30 days of the start of the Baseline Assessment Period.
8. Diagnosis of osteoarthritis of the knee or hip as defined by the American College of Rheumatology (ACR) combined clinical and radiographic criteria (refer to [Appendix 4](#)); Radiographic criteria will be assessed by the Central Reader.

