#### **5.8.1.3. Restrictions on Use of Treatments for Underlying Cancer or Bone Metastasis**

Monoclonal antibodies used for the treatment of underlying cancer (eg, bevacizumab (Avastin), trastuzumab (Herceptin), panitumumab (Vectibix)) or bone metastasis (eg, denosumab (Prolia, Xgeva)) are generally permitted if ongoing at stable dose regimen at least 30 days prior to the first day of the Baseline Assessment Period (see [Section 5.8.2.3](#)). However, monoclonal antibody therapies associated with clinically significant peripheral or autonomic neuropathy or joint-related adverse effects or those based on chimeric or murine antibodies (eg, cetuximab (Erbix)) are prohibited within 90 days of the start of the Baseline Assessment Period and during the study until Week 32. Monoclonal antibody therapies which are not specifically listed as permitted (see [Appendix 8](#)) should be discussed with the study clinician on a case-by-case basis.

Small molecule inhibitors (eg, erlotinib (Tarceva), sunitinib (Sutent), lapatinib (Tykerb)) used in the treatment of underlying cancer or bone metastasis are permitted (except for bortezomib) if at a stable dose regimen at least 30 days prior to the first day of the Baseline Assessment Period.

If during the double-blind treatment period prior to Week 8, the subject's underlying cancer or bone metastasis progresses so as to require a new chemotherapy regimen, new concomitant bisphosphonates, new concomitant hormonal anti-cancer treatment, or initiation of radiotherapy to sites of bone metastasis, the subject should be withdrawn from study treatment (eg, due to disease progression) and entered in the Early Termination Follow-Up period (refer to [Section 6.4](#)). Between Week 8 to Week 32, if treatment for underlying cancer

or bone metastasis needs to be initiated or changed (refer to [Section 5.8.2.3](#)), the study clinician should be informed so that guidance may be provided as to whether the subject should be withdrawn from study treatment and entered in the Early Termination Follow-Up period. After the Week 32 visit, standard of care treatment may be prescribed as appropriate, without prior consultation with the study clinician.

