#### **5.8.2.3. Permitted Concomitant Treatments for Underlying Cancer or Bone Metastasis**

Concomitant anticancer treatment of the subject’s underlying primary cancer or bone metastasis is permitted as follows:

- Concomitant chemotherapy, other than paclitaxel, docetaxel, oxaliplatin, cisplatin, vincristine, thalidomide and bortezomib or those expressly prohibited (see Appendix 8), is allowable provided it was ongoing for at least 30 days before the first day of the Baseline Assessment Period. It is acceptable for the regimen to complete at any time after Randomization.
  - Paclitaxel, docetaxel, oxaliplatin, cisplatin, vincristine, thalidomide and bortezomib are not permitted from 30 days prior to the first day of the Baseline Assessment Period to Week 48.

- A subject with chemotherapy-induced peripheral neuropathy can be enrolled provided the neuropathy has been stable over the 6 months prior to the start of the Baseline Assessment Period and the subject is no longer being treated with a chemotherapy agent associated with peripheral neuropathy.
- Monoclonal antibody therapies used in the treatment of underlying cancer or bone metastasis are allowed (with some exceptions; refer to [Section 5.8.1.3](#)) if part of a stable dose regimen started at least 30 days prior to the first day of the Baseline Assessment Period. It is acceptable for the regimen to complete at any time after Randomization; however, if new treatment is initiated prior to Week 8, the subject should be withdrawn from study treatment. Refer to [Appendix 8](#).
  - Monoclonal antibody therapies associated with clinically significant peripheral or autonomic neuropathy or joint-related adverse effects or those based on chimeric or murine antibodies (eg, cetuximab (Erbix)) are prohibited within 90 days of the start of the Baseline Assessment Period and during the study until Week 32. Refer to [Section 5.8.1.3](#).
- Small molecule inhibitors used in the treatment of underlying cancer or bone metastasis (eg, erlotinib (Tarceva), sunitinib (Sutent)) are permitted (except for bortezomib) during the study if initiated at least 30 days prior to the first day of the Baseline Assessment Period and maintained at stable dose during the double-blind treatment period to at least Week 8.
- Blood and blood products for transfusion are allowed throughout the study.

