## 9.7.1. Protocol-Level Rules for Dosing Suspension/Safety Assessments

### 9.7.1.1. Serious Adverse Events

Tanezumab safety will be reviewed at two levels; blinded data reviews by Pfizer and unblinded reviews by the E-DMC. The E-DMC will review unblinded safety data including adverse events and serious adverse events on a regular basis throughout the course of these studies. Pfizer performs blinded review of all serious adverse event data (including those serious adverse events specified below) and a cumulative review on a monthly basis. If blinded review notes a pre-specified serious adverse event occurring at a rate that could trigger the protocol-based dosing suspension rule (ie, at least 3 or more cases of a given pre-specified serious adverse event), an urgent, ad hoc assessment by the E-DMC will be conducted. The E-DMC will determine whether a protocol-based dosing suspension rule should be triggered. At the individual protocol-level, if a given pre-specified serious adverse event is reported in 3 more subjects in any individual tanezumab treatment group than for placebo-treated subjects, the protocol-based rule for dosing suspension will be triggered.

The pre-specified serious adverse events are:

- Sudden cardiac death or cardiac death;
- Acute renal failure;
- Anaphylactic shock or severe anaphylactic reaction;
- Neuropathic joint or neuropathic arthropathy (ie, Charcot joint);
- Autonomic or peripheral neuropathy confirmed with objective findings such as treatment-emergent abnormalities on **CCI** nerve conduction abnormalities or biopsy findings consistent with peripheral neuropathy.

If a protocol-based rule for dosing suspension is triggered, it will result in suspension of further dosing of subjects in the study until a decision is reached regarding whether it is safe to resume dosing in some or all treatment groups or whether the study should be terminated completely. This decision will be made by the sponsor in consultation with the tanezumab E-DMC. Factors that may be considered in making this decision in relation to serious adverse events or adjudicated clinically significant adverse events include:

- Consideration of relationship of study medication to the adverse event;
- Consideration of whether similar adverse events are occurring in other tanezumab studies with similar subject populations;
- Dosage of tanezumab (10 mg or 20 mg) and distribution of adverse events across tanezumab dose arms;

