### **Chemotherapeutic, Radiopharmaceutical or Radiotherapy, Anti-Cancer Hormonal Treatments**

Concomitant chemotherapy is allowable, with some exceptions (see Section 5.8.2.3.), provided it was ongoing for at least 30 days before the first day of the Baseline Assessment Period. It is acceptable for the regimen to complete at any time after Randomization.

- A subject with chemotherapy-induced peripheral neuropathy can be enrolled provided the neuropathy has been stable over the 6 months prior to the start of the Baseline Assessment Period and the subject is no longer being treated with a chemotherapy agent associated with peripheral neuropathy (i.e. paclitaxel, docetaxel, oxaliplatin, cisplatin, vincristine, thalidomide and bortezomib).
- Chemotherapies associated with peripheral neuropathy (i.e. paclitaxel, docetaxel, oxaliplatin, cisplatin, vincristine, thalidomide and bortezomib) are not permitted from 30 days prior to the first day of the Baseline Assessment Period to Week 48 regardless of symptomatology.

Receipt of radiopharmaceutical treatment or radiotherapy for treatment of bone metastasis within 30 days of the first day of the Baseline Assessment Period and through to Week 8 is not permitted.

Concomitant hormonal anti-cancer treatment (eg, GnRH agonists or antagonists, anti-androgens or anti-estrogens) is allowable if treatment has been ongoing at stable dose for at least 30 days prior to the first day of the Baseline Assessment Period. Post Baseline, the concomitant hormonal anti-cancer treatment dose regimen should remain stable until at least Week 8.

If prior to Week 8, the subject's underlying cancer or bone metastasis progresses so as to require a new chemotherapy regimen, new concomitant bisphosphonates, new concomitant hormonal anti-cancer treatment, or initiation of radiotherapy to sites of bone metastasis, the subject should be withdrawn from study and entered in the Early Termination Follow-Up period (refer to [Section 6.4](#)).

Following the Week 8 visit, standard of care treatments may be initiated (refer to [Section 5.8.2.3](#)).

Criteria for Use of Chemotherapeutic, Radiopharmaceutical/ Radiotherapy or Hormonal Treatments*		
Therapy	Permitted	Prohibited

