Chemotherapy (see below for criteria regarding biologics)	Allowable, with some exceptions (see Section 5.8.2.3.), if ongoing for at least 30 days before start of Baseline Assessment Period.	If a new chemotherapy regimen is required prior to Week 8, subject should be withdrawn and entered in the Early Termination Follow-Up period (refer to Section 6.4).  Chemotherapies associated with peripheral neuropathy (i.e. paclitaxel, docetaxel, oxaliplatin, cisplatin, vincristine, thalidomide and bortezomib) are not permitted from 30 days prior to the first day of the Baseline Assessment Period to Week 48 regardless of symptomatology .
Radiopharmaceutical treatment or radiotherapy for bone metastasis	Permitted if $\geq 30$ days prior to first day of the Baseline Assessment Period.	Prohibited within 30 days of the first day of the Baseline Assessment Period through to Week 8.  If initiation of radiotherapy to sites of bone metastasis or new radiopharmaceutical regimen is required prior to Week 8, subject should be withdrawn and entered in the Early Termination Follow-Up period (refer to Section 6.4).
Concomitant hormonal anti-cancer treatment (eg, GnRH agonists or antagonists, anti-androgens or anti-estrogens)	Permitted if ongoing at stable dose for $\geq 30$ days prior to first day of Baseline Assessment Period.	Post-Baseline, should remain stable until at least Week 8.  If initiation of new concomitant

		hormonal anti-cancer treatment is required prior to Week 8, subject should be withdrawn and entered in the Early Termination Follow-Up period (refer to Section 6.4).
--	--	---

\*Following the Week 8 visit, standard of care treatments may be initiated (refer to Section 5.8.2.3).

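### Seven neuropathy-associated chemotherapies are barred to Week 48, but two sections release cancer treatment after Week 32 without excepting them, and nothing says which rule governs

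*Protocol*

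**What the plan says.** **The bar.** Exclusion criterion 5 (Section 4.2) names the seven agents as chemotherapies associated with peripheral neuropathy and says they "are prohibited during study period from 30 days prior to the first day of the Baseline Assessment Period to Week 48". Section 5.8.2.3 repeats the list, ending "thalidomide and bortezomib are not permitted from 30 days prior to the first day of the Baseline Assessment Period to Week 48". Appendix 8 says that they "are not permitted from 30 days prior to the first day of the Baseline Assessment Period to Week 48 regardless of symptomatology", and repeats the bar in its chemotherapy table and, in part, in its biologics table.

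**The release after Week 32.** Section 5.8.2.6 states "Following Week 32, cancer or bone metastasis treatment may be instituted in accordance with standard of care without prior consultation of the study clinician". Section 5.8.1.3, the section on restrictions, states "After the Week 32 visit, standard of care treatment may be prescribed as appropriate, without prior consultation with the study clinician".

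**The release from Week 8.** Section 6.2.2.2 lets the investigator change cancer or bone metastasis therapy from Week 8 and names only NSAIDs as an exception. The chemotherapy part of Appendix 8 says "Following the Week 8 visit, standard of care treatments may be initiated", in the text and again in the table footnote, and both refer the reader to Section 5.8.2.3. The biologics part has a similar sentence without that reference. For Weeks 8 to 32, Sections 5.8.1.3, 5.8.2.6 and 6.2.2.2 ask that the study clinician be informed.

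**The safety context.** Section 9.4 summarises adverse events of abnormal peripheral sensation. Section 9.6 has safety data collected to the end of Week 48.

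**The concern.** A site deciding on cancer treatment during safety follow-up would naturally look at Section 5.8.2.6, whose title covers exactly that decision. Read on its own, the post-Week-32 sentence permits any standard-of-care regimen, including a listed agent, with no call to the study clinician. A site that looks at Section 5.8.2.3 or Appendix 8 finds the same agent barred for another 16 weeks.

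Two things are at stake. Sites have contradictory instructions on cancer care. And the bar concerns drugs that the protocol itself links to peripheral neuropathy, in a trial that follows neuropathy as a safety question to Week 48. If some sites follow the bar and others the release, part of the late neuropathy data will reflect chemotherapy. Similar use in both arms mainly adds noise; unequal use would bias the comparison.

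**Working it through.** The plan states no figure to reproduce here. The check sets the passages side by side and then uses the study days in Table 1 of the protocol.

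**Passages compared for one listed agent**

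| Place | Weeks 8 to 32 | Weeks 32 to 48 |
|---|---|---|
| 4.2 criterion 5; 5.8.2.3; Appendix 8 chemotherapy table | barred | barred |
| 5.8.1.3, 5.8.2.6 | clinician informed; refers to 5.8.2.3 | released; no consultation, no exception, no reference |
| 6.2.2.2 | changes allowed, only NSAIDs excepted; clinician informed | not separately addressed |
| Appendix 8 chemotherapy footnote | released, refers to 5.8.2.3 | same |
| Appendix 8 biologics sentence | released, no reference in the sentence | same |

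In Sections 5.8.1.3 and 5.8.2.6 the reference to Section 5.8.2.3 sits in the Week 8 to 32 sentence. The post-Week-32 sentence has none. Section 5.8.1.3 does except bortezomib when it discusses small molecule inhibitors, but that exception is not carried into its post-Week-32 sentence and does not cover the other six agents. No passage says whether the specific bar or the general release prevails.

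**Length of the direct conflict**

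- Inputs: randomisation Day 1, Week 32 = Day 225, Week 48 = Day 337.
- Post-randomisation time: 337 − 1 = 336 days.
- Conflict: 337 − 225 = 112 days, and 112/336 = 33%.

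**Where this falls relative to dosing**

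- The third dose is nominally on Day 113 (Week 16). Week 32 is 225 − 113 = 112 days later.
- With the half-life of about 21 days in Section 3: 112/21 = 5.3 half-lives, and 0.5^5.33 ≈ 2.5% remaining.
- The direct conflict therefore lies in safety follow-up, after most of the drug has gone and long after the Week 8 primary endpoint.

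**Early terminators**

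- They are followed for about 24 weeks after the last dose (Section 6.4). With last doses at Day 1, Week 8 or Week 16, follow-up nominally ends near Week 24, 32 or 40.
- All three fall before Week 48, so the stated end of the bar is never reached on their schedule.
- For opioid–NSAID combinations (Section 5.8.1.1) and for NSAIDs and intra-articular corticosteroids (Section 5.8.2.5), the protocol gives Week 32 together with its counterpart, the second early-termination visit. It gives no counterpart for the listed chemotherapies.

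**The case against.** The strongest reply is that a specific bar overrides a general release. The bar names its agents, gives a start and an end, and is repeated several times. The Week 32 sentences can be read as removing only the need to consult, not the bar. Section 5.8.2.3 lies in the same block as Section 5.8.2.6, so a careful site would see it. This reading is reasonable, but the protocol does not state it, and in the two post-Week-32 sentences nothing leads a reader to it.

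Three stronger readings are tempting and are not supported.

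- *The conflict runs from Week 8, for 280 of 336 days (83%).* The chemotherapy footnote in Appendix 8 refers to the section that holds the bar, and the clinician is to be informed until Week 32. That contact is described as guidance on withdrawal from study treatment rather than as a check for barred agents, so a gap remains, but it is weaker than the later one.
- *One or two chemotherapy cases could trigger or mask the dosing-suspension rule.* Section 9.7.1.1 does list "Autonomic or peripheral neuropathy confirmed with objective findings" among its pre-specified serious events, with a threshold of 3 more subjects than placebo. But the event must be serious and objectively confirmed, the E-DMC decides on unblinded data, and relationship to study medication and concomitant medication are listed factors in the decision that follows a suspension. The documents give no basis for sizing an effect on the rule.
- *The neuropathy comparison is confounded.* Confounding needs sites to act on the release and use to differ between arms. Allocation is randomised and blinded, and the documents do not show unequal use.

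On early terminators, the bar can be read as covering their whole follow-up, since criterion 5 speaks of the study period. The missing end point is a gap in wording, not a separate contradiction.

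**Conclusion.** The contradiction stands for Weeks 32 to 48: Sections 5.8.1.3 and 5.8.2.6 release what criterion 5, Section 5.8.2.3 and Appendix 8 bar, and no order of precedence is given. The 33% measures how long the wording overlaps; it is not an effect size. The documents do not say how many subjects might start a listed agent in that window, so the effect on the neuropathy data cannot be quantified.

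The consequence is possible inconsistency between sites, and with it noise or possible bias in neuropathy data collected to Week 48. It rests on the assumption that at least some sites would act on the release as written. The Week 8 primary endpoint is unaffected. Section 6.2.2.2 and the biologics text carry a weaker version of the same gap from Week 8. The correction is worth making because it changes what sites are told they may do.

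**What to change.** Reconcile the passages to one stated rule and one end point for the listed agents. Which rule and which end point is for the clinical team; this review proposes neither. Then:

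- cross-reference that rule in Sections 5.8.1.3, 5.8.2.6 and 6.2.2.2 and in the chemotherapy and biologics parts of Appendix 8;
- state the equivalent end point for early terminators, in the form already used for NSAIDs.

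The cost is a few lines of protocol wording and a note to sites, with no new data and no change to sample size or the primary analysis. No extra neuropathy analysis with and without subjects who received a listed agent is asked for. It would be a matter for the SAP, and removing events according to a treatment chosen after randomisation could itself bias the comparison.

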## **6. STUDY PROCEDURES**

Refer to Schedule of Activities [Table 1](#) and [Table 2](#) for the lists of procedures to be performed throughout the study.

As a general rule, scales/instruments should be completed first by the subject upon arrival at the clinic and vital signs should be assessed prior to blood draws. If possible, each subject's clinic visits should be conducted at approximately the same time of day.

Subjects should be thoroughly instructed on completion of the scales/instruments via IRT prior to completing them the first time (at Screening for PGA of Cancer Pain **CCI** at Baseline for **CCI** OR-SDS **CCI** questionnaires). No coaching or other interpretative assistance should be given to subjects during completion of these questionnaires.

The windows for study visits (in clinic and phone contacts) are  $\pm 3$  days for the Week 2 to Week 16 visits,  $\pm 5$  days for the Week 20 to Week 28 visits, and  $\pm 7$  days for the Week 32 to Week 48 visits. Study visits should be scheduled with reference to the study drug dosing date as much as possible. Subject scheduling issues should be brought to the attention of the study monitor for resolution. Dosing visits should occur no earlier than 7 weeks from the previous injection. The visit window for the Week 24 x-rays is  $\pm 30$  days from the nominal time point of the visit. The Week 48 x-rays should be obtained within a  $\pm 30$  day visit window, preferably prior to the Week 48 visit, but if possible, no more than 14 days after the Week 48 visit. In Japan only, the Week 16 x-rays may be obtained up to 7 – 21 days before the Week 16 visit (Week  $14 \pm 7$  days).

